This will be an open-label, single-arm, multicenter, 2-year Phase IV trial. Subjects meeting the eligibility criteria during a pre-baseline screening period of up to -3 months before baseline (Day 1 of treatment) will receive an initial treatment course in Year 1 and a retreatment course in Year 2.

Subjects will attend visits for assessments at end of Months 1,2,3,6, 12 following Baseline (Day 1 of treatment) and at end of Month 15,18, 24 following second treatment course (Month 1 of Year 2), respectively. Subjects will attend visits for blood sample as per mandatory monitoring at pre-Baseline and at Months 2, 6, 12, 14, 18 and 24. The primary endpoint(s) will be assessed during the first 6 months, secondary and tertiary endpoints will be assessed up to Month 24.

CCI [REDACTED]

Visit schedules for efficacy and safety assessments are detailed in the Schedule of Assessments.

Planned number of subjects: Approximately 265 subjects are planned to be included

Primary endpoint(s):

- Differences in the counts of combined unique active (CUA) MRI lesions during the first 6 months (i.e. during periods months 1-6, 2-6, 3-6) compared to baseline (i.e. the period screening to baseline)

Secondary endpoints:

- Characterization of immune cell subsets count at the end of 3, 6, 12, 15, 18 and 24 months compared to baseline

Tertiary endpoints:

Safety:

- Occurrences of treatment-emergent adverse events (TEAEs) and serious adverse events (SAEs) including and up to 24 months

Clinical:

- Changes in Symbol Digit Modality Test (SDMT) outcome at the end of 6, 12, 18 and 24 months compared to baseline
- Disability evolution as measured by Expanded Disability Status Scale (EDSS)/ Kurtzke Functional System (KFS), 9-Hole Peg Test (9HPT), Timed 25-Foot Walk (T25FW) at the end of 6, 12, 18 and 24 months compared to baseline
- Annualized Relapse Rate (ARR) between baseline and 24 months
- Changes in CUA lesions during the following post-baseline periods –compared to baseline period (i.e. the period from screening to baseline):
 - Period of month 6 to month 12
 - Period of month 1 to month 12
 - Period of month 18 to month 24
 - Period of month 1 to month 24Further periods and comparisons may be defined in the SAP
- Number of CUA lesions during the baseline and post-baseline periods as defined above
- Changes in active T1 gadolinium (Gd)+ lesion count at the end of 1, 2, 3, 6, 12, 15, 18 and 24 months compared to baseline

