Subjects who discontinue cladribine tablets at any time during the trial will continue to participate in the scheduled visits for assessments until his/her planned trial completion. In the event of early discontinuation from the trial, the subject should return for the Early Termination visit for final assessment.

For subjects who experience a relapse and initiated on another DMD (as per investigator's discretion), the subject will not participate further in any trial assessments and be followed-up by the investigator as standard of routine practice. The subject should however complete the early termination visit for final assessment.

Withdrawn subjects will not be replaced.

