8.5 Description of Statistical Analyses

8.5.1 General Considerations

All analyses of all endpoints except the primary analysis, will be performed exploratively and, differences with a p-value of 0.05 or less will be considered nominally statistically significant.

Parameter estimates with associated 95% confidence intervals (CIs) will be reported in each analysis. No correction for multiple testing will be applied for any secondary or tertiary analysis.

Subjects' demographic factors and baseline clinical characteristics will be summarized with the following measures: mean with standard deviation, minimum and maximum for normally distributed continuous variables, median with interquartile range, minimum and maximum for other continuous variables and counts with percentages for categorical variables.

As the secondary and tertiary analysis set concerns repeated measurements of outcomes for each individual, it is likely that observations pertaining to each individual will be correlated. Furthermore, as this is a multi-center trial, it is likely that clustering of individuals within trial sites will produce an additional source of correlation. Mixed-effects regression, whereby a three-level hierarchical model is specified for observations within subjects within trial sites, will be used to account for within-subject and within-center correlation (Gibbons, 2010).

The parametric assumptions underlining the regression models specified will be examined. Should these assumptions be violated, alternative methods, such as non-parametric approaches, may be considered in addition.

Assessment Schedules

It is likely that the second year treatment may be delayed substantially due to grade 3 or 4 lymphopenia for a small number of subjects for whom the second dose is not required immediately. Due to the need for a finite follow-up period, a buffer of 3 months is given for subjects who do not receive the second treatment at the specified time. Subjects for whom treatment is delayed by over 3 months may not have all assessment data captured and as such, these observations will be treated as missing in efficacy analyses.

In each analysis, should assessment be delayed, subjects' assessment data will be treated as though it occurred at the time point specified and inferences will be conducted accordingly.

Missing Data

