The last non-missing measurement prior to start of study medication will serve as the Baseline measurement. Measurements performed on the day of first intake of study medication are assumed to be “prior to start of study medication”, as long as it has not been confirmed that the procedure was performed afterwards. This assumption is justified as following the sequence of procedures as specified in the study protocol. The intake of study medication should be the last procedure on the Visit day.

The MRI scans will be reconciled during central MRI review process. Therefore, MRIs will be considered as Baseline MRIs if assigned to the Baseline Visit by the central imaging review.

Definition of Study Periods

- Baseline Period: The Baseline Period is defined as the Period between the Screening and the Baseline MRI scan.
- Post-Baseline Period: The post-Baseline Periods that are used in the primary analysis are defined as follows:
 - Period 1 (p₁) is defined as the Period between Month 1 and Month 6 MRI scans.
 - Period 2 (p₂) is defined as the Period between Month 2 and Month 6 MRI scans
 - Period 3 (p₃) is defined as the Period between Month 3 and Month 6 MRI scans

In addition, the following post-Baseline Periods are defined solely for tertiary analyses:

Three months Periods

- Period 3.1 (p_{3.1}) is defined as the Period between Baseline and Month 3 MRI scans.

Six months Periods

- Period 6.1 (p_{6.1}) is defined as the Period between Baseline and Month 6 MRI scans,
- Period 6.2 (p_{6.2}) is defined as the Period between Month 6 to Month 12 MRI scans,
- Period 6.3 (p_{6.3}) is defined as the Period between Month 12 to Month 18 MRI scans,
- Period 6.4 (p_{6.4}) is defined as the Period between Month 18 to Month 24 MRI scans.

Periods excluding the Period between the Baseline scan and the Month 1 MRI scan:

- Period 11.1 (p_{11.1}) is defined as the Period between Month 1 to Month 12 MRI scans,
- Period 11.2 (p_{11.2}) is defined as the Period between Month 1 to Month 24 MRI scans.

Yearly Periods:

- Period 12.1 (p_{12.1}) is defined as the Period between Baseline to Month 12 MRI scans,
- Period 12.2 (p_{12.2}) is defined as the Period between Month 12 to Month 24 MRI scans.

2 -Year Period:

- Period 24.1 (p_{24.1}) is defined as the Period between Baseline to Month 24 MRI scans.

Sequential Visit Periods

- Period 100.0 (p_{100.0}) is defined as the Period between Screening and Baseline (equivalent to Baseline Period) MRI scans

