Note: the number of new or enlarging T2 (with and without T1 Gd+) will be provided by central reading for each of the Periods including the Sequential Visit Periods, except for Period 3.1. For Period 3.1, the sum of the Sequential Visit Periods 100.1, 100.2 and 100.3 will be calculated.

For the calculation of the CUA lesion count, only T2 lesions that did not emerge from a T1 Gd+ lesion will be taken into account.

- Total active T2 lesion count (without T1 Gd+) =
Total new T2 lesion count without T1 Gd+
+ Total enlarging T2 lesion count without T1 Gd+

and will be standardized to the length of the Period (i.e. annualized). Total active T2 lesion count (without T1 Gd+) will only be calculated if T1 Gd+ counts for beginning and end of the corresponding Period are non-missing.

CUA lesion count

The number of CUA lesions for a Period will be defined as the sum of the T1 Gd+ and new or enlarging T2 counts for the respective Period and will be standardized to one scan (for T1) or one year (for T2) to harmonize the units of the 2 assessments.

$\#CUA(p_{\text{post-Baseline}})$ = Annualized CUA lesion count (by post-Baseline Period per 1 year)
= Mean T1 Gd+ lesion count (by Period i)
+ Annualized total active T2 lesion count (without T1 Gd+)
(by Period i per 1 year) Different from the primary analysis, T2

lesion count will be standardized to 1 year instead of 1 month due to longer periods and for comparison with other studies,

The CUA lesion count will only be calculated if both components (T1 and T2) are non-missing.

Data Handling in case of major PDs

PDs will not be considered in the planned statistical analyses (i.e., all data will be analyzed independent from any reported PD) except for PD due to MRI taken during steroid treatment (MRI will be excluded from the primary analysis).

Covariates and stratification factors

Age

Age (years) at time of Informed Consent (loaded from iRT). Missing age will be replaced as follows if used as a covariate:

- Age will be estimated from the year of birth (year of IC – year of birth), as recorded in the electronic Case Report Form (eCRF),
- If year of birth is missing, age will be imputed by the mean age of the FAS.

EDSS at Baseline

Expanded Disability Status Scale (EDSS) at Baseline will be categorized by:

- ≤ 3 (reference),
- >3 .

Missing EDSS at Baseline will be imputed by the median Baseline EDSS of the FAS if used as a stratification factor.

Pooled centers

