Primary (FAS)	
 1. Period 3 (Month 3-6): $\Delta\text{CUA}(p_3)$ (Hypothesis 3) 2. Period 2 (Month 2-6): $\Delta\text{CUA}(p_2)$ (Hypothesis 2) 3. Period 1 (Month 1-6): $\Delta\text{CUA}(p_1)$ (Hypothesis 1) 	
P-values for the three Hypotheses from the Wilcoxon signed-rank test will be presented. The testing procedure will stop as soon as one of the hypotheses cannot be rejected following the pre-specified order (H3, H2, H1). Due to this sequential order of tests an adjustment for a potential type-I-error inflation due to the multiple testing is not required.
 
The Wilcoxon signed-rank test will be complemented by the estimated Least Square Means (LS Means) and corresponding Standard Errors (SE) including one-sided p-values as well as two-sided p-value and 95% CIs from the mixed-effects linear model with the following adjusting factors:
 
 • Baseline score, • Age (in years), • EDSS at Baseline (≤ 3, >3), • Within-pooled center correlation. 
In addition, the distribution of $\text{CUA}(p_i)$ and $\Delta\text{CUA}(p_i)$ will be displayed graphically using box plots.
	
Missing observations: Subjects with a missing CUA lesion count at either the Baseline Period or the respective post-Baseline Period will not be included in the analysis.

$\Delta\text{CUA}(p_i)$ = Difference in the standardized CUA lesion count between Period i and the Baseline Period (a) 6-month interim analysis
			

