14.3 Tertiary Endpoints

14.3.1 Changes in CUA lesion count

The changes in CUA lesion counts from the Baseline Period to the post-Baseline Periods are defined in the Section 9 “Definition of Study Periods” and “Data Handling of MRI data”.

CUA lesion counts will further be classified for each Period as follows:

- CUA lesion count > 0
 - Yes (CUA lesion count > 0)
 - No (CUA lesion count = 0)

Analysis (Analysis Set)	Derivation	Statistical Analysis Methods	Missing data handling
Tertiary endpoints: Change from the Baseline Period in Annualized CUA lesion count to the six months post-Baseline Periods			
Tertiary (FAS)	Period 6.1 (Baseline-Month 6): $\Delta\text{CUA}(p_{6.1})$	Mixed-effects linear model for repeated measures with the following adjusting factors: 
 • Baseline score, • Age (years), • EDSS at Baseline (≤ 3, > 3), • Period, • Pooled center • Within-subject correlation. Estimated Least Square Means (LS Means) and corresponding Standard Errors (SE) will be presented by Period including 2-sided p-values and 95% CI.	Missing observations at Baseline: Subjects with a missing Baseline score will not be included in the linear model. Missing post-Baseline observations: Missing post-Baseline assessments will not be imputed. The repeated measurement model handles missing post-Baseline assessments under the assumption of MAR.
Tertiary (FAS by subgroup "High-relapse activity")	Period 6.2 (Month 6-12): $\Delta\text{CUA}(p_{6.2})$		
Tertiary (FAS by subgroup "Previous treatment with DMDs")	Period 6.3 (Month 12-18): $\Delta\text{CUA}(p_{6.3})$		
	Period 6.4 (Month 18-24): $\Delta\text{CUA}(p_{6.4})$		
Tertiary endpoints: Ratio of the six months post-Baseline Periods versus the Baseline Period in Annualized CUA lesion count			
Tertiary (FAS)	Period 6.1 (Baseline-Month 6): $\# \text{CUA}(p_{6.1})/\# \text{CUA}(p_0)$	Generalized model assuming a negative binomial distribution with the following adjusting factors: 
 • Age (years), • EDSS at Baseline (≤ 3, > 3), • Period, • Within-subject correlation. Estimated standardized CUA for the Periods as well as the ratios of each post-Baseline Period versus the Baseline Period, and corresponding Standard Errors (SE) will be presented including estimated fixed effects including the SE, 2-sided p-values and 95% CI	All data available will be used in the model.

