Tertiary (FAS by subgroup "High-relapse activity")	Period 6.2 (Month 6-12): $\# \text{CUA}(p_{6.2})/\# \text{CUA}(p_0)$		
Tertiary (FAS by subgroup "Previous treatment with DMDs")	Period 6.3 (Month 12-18): $\# \text{CUA}(p_{6.3})/\# \text{CUA}(p_0)$		
	Period 6.4 (Month 18-24): $\# \text{CUA}(p_{6.4})/\# \text{CUA}(p_0)$		
Tertiary endpoints: Change from the Baseline Period in Annualized CUA lesion count to the yearly post-Baseline Periods			
Tertiary (FAS)	Period 12.1 (Baseline-Month 12): $\Delta\text{CUA}(p_{12.1})$	Mixed-effects linear model for repeated measures as specified above.	Same as above for the mixed effect linear model with repeated measures.
Tertiary (FAS by subgroup "High-relapse activity")	Period 12.2 (Month 12-24): $\Delta\text{CUA}(p_{12.2})$		
Tertiary (FAS by subgroup "Previous treatment with DMDs")			
TCS-1			
TCS-2			

Analysis (Analysis Set)	Derivation	Statistical Analysis Methods	Missing data handling
Tertiary endpoints: Ratio of the yearly post-Baseline Periods versus the Baseline Period in Annualized CUA lesion count			
Tertiary (FAS)	Period 12.1 (Baseline-Month 12): #CUA(p12.1)/#CUA(p0) Period 12.2 (Month 12-24): #CUA(p12.2)/#CUA(p0)	Generalized model as specified as above.	Same as above for the generalized model.
Tertiary (FAS by subgroup "High-relapse activity")			
Tertiary (FAS by subgroup "Previous treatment with DMDs")			
Tertiary endpoint: Change from the Baseline Period in Annualized CUA lesion count to the 2-year post-Baseline Period			
Tertiary (FAS)	Period 24.1 (Baseline-Month 24): ΔCUA(p24.1)	Mixed-effects linear model with the following adjusting factors: 
 • Baseline score, • Age (years), • EDSS at Baseline (≤3, > 3), • Pooled center Estimated Least Square Means (LS Means) and corresponding Standard Errors (SE) will be presented including 2-sided p-values and 95% CI.	Same as in the Primary Analysis (see Section 14.1.1)
Tertiary (FAS by subgroup "High-relapse activity")			
Tertiary (FAS by subgroup "Previous treatment with DMDs")			
Tertiary endpoints: Ratio of the 2-year post-Baseline Period versus the Baseline Period in Annualized CUA lesion count			

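### The linear models for change in CUA (Periods 24.1, 11.1, 11.2) and in active T2 (Period 24.1) are labelled FAS but are complete-case, with no sensitivity analysis

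*SAP*

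**What the plan says.** SAP Section 9 gives the window: Period 24.1 "is defined as the Period between Baseline to Month 24 MRI scans". Periods 11.1 and 11.2 run from the Month 1 scan to the Month 12 and Month 24 scans. In the same section, under the data handling for tertiary endpoints, the T2 part of CUA "will only be calculated if T1 Gd+ counts for beginning and end of the corresponding Period are non-missing", and CUA needs both its T1 and T2 parts. The active T2 count is a reading of the Period's last scan against its first, so it also needs both.

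The Period 24.1 row of SAP 14.3.1 is "Change from the Baseline Period in Annualized CUA lesion count to the 2-year post-Baseline Period". For this row and for the change in CUA over Periods 11.1 and 11.2, the missing-data column points to SAP 14.1.1: "Subjects with a missing CUA lesion count at either the Baseline Period or the respective post-Baseline Period will not be included in the analysis". SAP 14.3.7 sends the Period 24.1 change in active T2 back to 14.3.1, so it inherits that rule. All these rows are labelled FAS.

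Two provisions decide who lacks a Month 24 count. If a subject relapses and starts another DMD, Protocol 5.5.1 says "the subject will not participate further in any trial assessments", although an early termination (ET) visit is still requested. SAP Section 9 sets efficacy data after the Course 1 Treatment Period to missing when Course 2 is delayed by more than three months or never starts.

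The six-month, yearly and by-Visit rows of 14.3.1 work differently: "The repeated measurement model handles missing post-Baseline assessments under the assumption of MAR".

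**The concern.** The label says FAS, but the estimate describes subjects with a usable scan at both ends of the window. Protocol 8.5.1 expects missing outcome data over 24 months, and Protocol 8.5.2 gives drop-out for lack of efficacy as its example of data not missing at random. If leaving follows on-treatment activity, the remaining subjects look better than the treated population. Adjusting for Baseline count, age, EDSS and center, with margins set to the whole analysis set, removes only the part of leaving that those variables explain.

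The SAP uses partial follow-up elsewhere. Mean Gd+ per Period is taken over whatever scans exist (Section 9). The relapse model has a log-duration offset (14.3.18). The brain-atrophy classification falls back to Month 12 and then Month 6 (14.3.11). The multiple imputation in 14.1.2 covers only the six-month primary Periods. So nothing tests the exclusion at 24 months, and the two-year CUA and T2 changes may disagree with the six-month results beside them for reasons a reader cannot see. Month 1 to 12 and Month 1 to 24 are protocol-listed CUA windows (Protocol 4.3.1), and no MAR-based model estimates either of them.

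**Working it through.** The plan gives no figure to reproduce. Inputs from the documents are the scan schedule, the rules above and the planned size ("Approximately 265 subjects are planned to be included"). Dropout rates and lesion means over these Periods are not given, so every value of them below is an assumption.

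**1. Who is lost.** SAP Section 9 maps ET assessments to the nearest planned visit still missing, and central reading assigns the MRI scans. ET procedures include MRI (Protocol 7.1.12). If all earlier visits were attended, an ET scan after Month 18 can only map to Month 24. With leaving times uniform over 24 months (assumed), that is (24 − 18)/24 = 25% of leavers. For Period 11.1, an ET scan between Months 6 and 12 maps to Month 12 in the same way. The remaining leavers have no count. Subjects with a delayed or never-started Course 2 lose the 24-month Periods even if scanned at Month 24.

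**2. The negative binomial row.** It uses all available data, but a leaver without a Period 24.1 count adds only the Baseline Period count and no on-treatment information.

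**3. Unadjusted size.** Let d be the share without a usable count and k the leavers' residual annualized rate divided by that of the retained subjects, whose mean is m. The true mean is m[1 + d(k − 1)] and the complete-case mean is m, so

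understatement = d(k − 1) / [1 + d(k − 1)].

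For d = 0.10 and k = 3 this is 0.20/1.20 = 16.7%.

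| d | k = 0.5 | k = 1 | k = 2 | k = 3 | k = 5 |
|---|---|---|---|---|---|
| 5% | −2.6% | 0 | 4.8% | 9.1% | 16.7% |
| 10% | −5.3% | 0 | 9.1% | 16.7% | 28.6% |
| 20% | −11.1% | 0 | 16.7% | 28.6% | 44.4% |

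A negative sign means residual activity is overstated. At d = 20% the analysis holds 265 × 0.80 = 212 subjects.

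**4. After Baseline adjustment.** Simulations used 265 subjects, a Baseline mean of 4 and residual activity averaging 20% of Baseline.
- *Steep exit rule*, with exit probability proportional to the last count plus 0.2. At 5.5% loss the residual rate was 0.694 against a true 0.799, an understatement of 1 − 0.694/0.799 = 13%. At 12.7% loss it was 0.562 against 0.802, or 30%. The change itself was overstated by 3% and 7.5%. Letting a random quarter of leavers keep a Month 24 scan gave 10% and 21%.
- *Mild exit rule*, with risk rising linearly to threefold at four or more lesions. The understatement was 2.7% at 5.5% loss and 6.3% at 12.9%, and the change was overstated by 0.7% and 1.6%. Keeping Month 18 leavers through an ET scan gave 1.8% and 4.4%.
- *A separate frailty model*, unadjusted, with activity-driven exit and about 10% leaving: 4% to 11%, or 3% to 9% with late ET scans kept.

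**5. Whether averaged Periods equal the two-scan count.** They do not. Period 24.1 averages Gd+ over eight scans (Months 1, 2, 3, 6, 12, 15, 18, 24), so Months 1 to 3 carry 3/8 = 37.5%. In the mean of Periods 6.1 to 6.4 they carry (3/4) × (1/4) = 18.75%, and Months 6, 12 and 18 each enter twice. T2 lesions that enhance at intermediate scans, resolve or enlarge twice may also be counted differently.

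**The case against.** The best defence is that most of this is already covered. The same section pre-specifies MAR repeated-measures models for six-month, yearly and by-Visit CUA over the same 24 months, and 14.3.7 does so for T2. SAP 10.1 reports how many FAS subjects have counts in each Period, so the reduced number will be visible. Period 24.1 was added by the SAP and is not among the protocol's listed windows. Protocol 8.5.1 treats everything outside the primary analysis as exploratory: "differences with a p-value of 0.05 or less will be considered nominally statistically significant". All of that stands, and it limits the severity. It does not supply a two-year estimate that keeps leavers, nor one for the protocol-listed Month 1 to 12 and Month 1 to 24 windows, and SAP 10.1 does not ask for reasons for exclusion.

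Two stronger readings are tempting. The first is that everyone who leaves early is excluded. The documents do not support it: subjects who switch DMD are still asked to attend the ET visit, late ET scans can map to Month 24, and stopping cladribine does not by itself end the visits. The second is that residual activity is understated as a fact. The excluded group also includes pregnancy, loss to follow-up, consent withdrawal and delayed Course 2, which can follow slow lymphocyte recovery. The documents do not give these subjects' lesion activity.

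The steep exit rule is also severe. It makes a subject with five lesions (5 + 0.2)/(0 + 0.2) = 26 times as likely to leave as one with none, whereas the protocol ties exit to clinical events rather than lesion counts.

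**Conclusion.** The complete-case rule is confirmed from the text for CUA in Periods 24.1, 11.1 and 11.2, and by cross-reference for active T2 in Period 24.1. No sensitivity analysis accompanies it. The likely direction is understated residual activity, on the condition that leavers are more active on treatment than those retained. Under the assumed exit rules at roughly 5% to 13% loss, the size runs from about 2% to 30%. The effect on the change itself is smaller: up to 7.5% under the steep rule and 1.6% or less under the mild one. The bias vanishes if leavers are equally active and reverses if they are less active.

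A reader might infer that the trial's main result is affected. It is not, because the primary endpoint ends at Month 6 and these are exploratory tertiary analyses. The severity is modest.

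**What to change.** In SAP 14.3.1 and 14.3.7, add a two-year estimate beside the two-scan Period 24.1 result: the equally weighted average of the LS means for Periods 6.1 to 6.4 from the repeated-measures model already specified, fitted to all FAS subjects with a Baseline score.

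For Periods 11.1 and 11.2, add the time-weighted average of the Sequential Visit Periods from the by-Visit CUA model. By the schedule, the weights for Month 1 to 12 are 1, 1, 3 and 6 over 11 months. For Month 1 to 24 they are 1, 1, 3, 6, 3, 3 and 6 over 23 months.

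Label the two-scan Period 24.1, 11.1 and 11.2 results as complete-case, and report the number excluded by reason, with delayed or never-started Course 2 as its own category. Keep the two-scan results: the averages weight Gd+ scans differently and can count some lesions differently, so they are close to the two-scan quantity but not identical with it. The averages also rest on MAR.

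The cost is SAP wording, one contrast per model already planned and one exclusion table. No new MRI reading is needed.
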